4.2 Exclusion Criteria

Any of the following criteria will disqualify the patient from participation:

Target Disease Exceptions

1. Any other malignancy from which the patient has been disease-free for less than 2 years, except for non-melanoma skin cancer, or in situ carcinoma of any site.

Medical History and Concurrent Disease

2. Patients who have organ allografts.
3. Patients who have had a major surgical procedure, open biopsy, or significant traumatic injury with poorly healed wound within 6 weeks prior to first dose of study drug; or anticipation of need for major surgical procedure during the course of the study (other than defined by protocol); fine needle aspirations or core biopsies within 7 days prior to first dose of study drug. NOTE: Patients will be allowed to start cycle 1 day 1 therapy after 24 hours from pre-treatment biopsy.
4. Autoimmune disease: Patients with a history of inflammatory bowel disease (including crohn's disease and ulcerative colitis) are excluded from this study as are patients with a history of autoimmune disease (e.g., rheumatoid arthritis, systemic progressive sclerosis

- [scleroderma], systemic lupus erythematosus, autoimmune vasculitis [e.g., Wegener's granulomatosis]).
5. Known history of testing positive for human immunodeficiency virus (HIV) or known acquired immunodeficiency syndrome (AIDS).
 6. Any underlying medical condition, which in the opinion of the Investigator, will make the administration of study drug hazardous or obscure the interpretation of adverse events, such as a condition associated with frequent diarrhea.
 7. Patients who have had a history of acute diverticulitis, abdominal fistula, gastrointestinal perforation, intra-abdominal abscess, GI obstruction, abdominal carcinomatosis which are known risk factors for bowel perforation, should be excluded from the study.
 8. Patients who have a primary brain tumor (excluding meningiomas and other benign lesions), any brain metastases, leptomeningeal disease, seizure disorders not controlled with standard medical therapy, or history of stroke within the past year.
 9. History of serious systemic disease, including myocardial infarction or unstable angina within the last 12 months, history of hypertensive crisis or hypertensive encephalopathy, uncontrolled hypertension (blood pressure of >140/90 mmHg) at the time of enrollment, New York Heart Association (NYHA) Grade II or greater congestive heart failure, unstable symptomatic arrhythmia requiring medication (patients with chronic atrial arrhythmia, i.e., atrial fibrillation or paroxysmal supraventricular tachycardia are eligible), significant vascular disease or symptomatic peripheral vascular disease.
 10. Patients who have history of other diseases, metabolic dysfunction, physical examination finding, or clinical laboratory finding giving reasonable suspicion of a disease or condition that contraindicates the use of an investigational drug or that might affect the interpretation of the results of the study or render the subject at high risk from treatment complications.
 11. Patients who are on high dose steroid (e.g. > 10 mg prednisone daily or equivalent) or other more potent immune suppression medications (e.g. infliximab)
 12. Patients who have had influenza, hepatitis, or other vaccines within a month prior to initiation of study drugs.
 13. Patients who have clinical history of coagulopathy, bleeding diathesis or thrombosis within the past year.
 14. Patients who have serious, non-healing wound, ulcer, or bone fracture.

15. Pregnancy (positive pregnancy test) or lactation.
16. Patients with prior orthotropic liver transplantation.
17. Patients with cirrhosis and severe synthetic liver dysfunction (Child Pugh B-C).

Prohibited Therapies and/or Medications

18. Patients must not have received prior anticancer therapy with anti-CLTA-4 or anti-PD1 for HCC. Patients receiving any concomitant systemic therapy for HCC are excluded.
19. Patients must not be scheduled to receive another experimental drug while on this study.
20. Patients who require ongoing anticoagulation will be excluded. Only aspirin will be permitted. Pre and post-surgical prophylactic anti-coagulation treatment is permitted.
21. Patients must not require total parenteral nutrition with lipids.

Other Exclusion Criteria

22. Any patients who cannot be compliant with the appointments required in this protocol must not be enrolled in this study.

5.0 TREATMENT PLAN

5.1 Registration

This is a randomized preoperative pilot study evaluating nivolumab alone or in combination with ipilimumab in patients with resectable HCC. Patients will be registered by the responsible study nurse or research coordinator.

5.2 Data Collection

Data will be collected and stored in an approved database as required.

5.3 Study Design and Duration

This is a pilot, randomized, open-label study of preoperative nivolumab alone (Arm A) or nivolumab plus ipilimumab (Arm B) in patients with resectable HCC. **A total of 30 patients will be enrolled as follows: Arm A (15 patients) and Arm B (15 patients).** Patients will be randomized into either Arm A or B.

Note: As of January 8, 2020, 30 patients have been enrolled and 27 patients have been randomized. The PI decided to stop enrollment since the study has reached its primary endpoint of safety.

During screening, patients will be evaluated by a surgeon to determine if they are good candidates for conservative hepatic resection or liver resection with curative intent. All patients will also be required to provide a pre-treatment biopsy with documented tumor involvement by pathologist review.

Originally, this study included a third arm (Arm C) in which 15 unresectable patients were to receive nivolumab 240 mg IV every 2 weeks for 3 doses plus ipilimumab 1 mg/kg IV on day 1 of therapy (3 doses of nivolumab, 1 dose of ipilimumab; 6 weeks) followed by post-treatment biopsy. The study objective in Arm C was to estimate the conversion rate to surgery for potentially resectable patients. However, the study has been amended in June 2019 to remove exclude this objective and enrollment of Arm C (Appendix II).

Patients in **Arm A (resectable cohort)** will receive nivolumab at 240 mg IV every 2 weeks for 3 doses followed by liver imaging and hepatic resection on day 1 of week 7, followed (after 4 weeks from surgery) by nivolumab 480 mg IV every 4 weeks in the adjuvant setting until disease progression or for 2 years, whichever is sooner. Patients in **Arm B (resectable cohort)** will receive nivolumab 240 mg IV every 2 weeks for 3 doses plus ipilimumab 1 mg/kg IV on day 1 of therapy (3 doses of nivolumab, 1 dose of ipilimumab) followed by hepatic resection followed (after 4 weeks from surgery) by nivolumab 480 mg IV every 4 weeks plus ipilimumab 1 mg/kg IV every 6 weeks to 4 doses in the adjuvant setting. Adjuvant therapy will start after 4 weeks from surgery with nivolumab 480 mg IV every 4 weeks (Both Arms A and B) plus ipilimumab 1 mg/kg IV every 6 weeks (in Arm B only) for up to 4 doses in the adjuvant setting until disease recurrence or for total of 2 years from first cycle, whichever is sooner. For Arm B, ipilimumab will be administered before nivolumab since the toxicities for ipilimumab are already well-known. Since the doses of nivolumab and ipilimumab either as monotherapy or combination are within maximum tolerated doses as previously defined, no dose increases or reductions will be allowed.

Patients will return at week 6 for a pre-surgical evaluation. A small portion of patients with rapid disease progression (We anticipate 1-3 of a total of 30 patients in Arms A and B) may not have hepatic resection per discretion of the treating surgical and medical oncologists. These patients will be off protocol and treated with other standard or investigational agents. They will be asked to return for an optional biopsy that will be scheduled in place of their surgery. For patients who had significant progression of disease pre-operatively but are still eligible for hepatic resection or transplantation, they will be treated with other investigational agents vs. observation post-operatively as there is no standard adjuvant therapy in surgically resected HCC.

After finishing the last treatment, hepatic resection or biopsy will occur on day 1 of week 7 (+/- 7 days). We will obtain surveillance scans (MRI of abdomen and pelvis with/without contrast, and CT chest with/without contrast of chest) 8 weeks after surgery. Patients who show significant progression of disease post-operatively will be taken off study and an optional biopsy will be taken at that time for immunological analysis.

Patients who complete the study or discontinue study treatment should be scheduled for an end of treatment visit (EOT) as soon as possible. All patients who complete the study or discontinue treatment will have a safety follow-up visit 30 (+/- 14 days) after the last dose of study drug or surgery, whichever comes last. Please refer to **Figure 2** below for the study design.

Patients will receive baseline staging studies with CT or MRI and be assessed for treatment response by scans: MRI or CT of abdomen and pelvis with/without contrast, and CT chest with/without contrast of chest (according to RECIST 1.1 and irRC) at week 6 (+/- 7 days). Each patient will have post-surgical (day 1 of week 11 +/- 7 days), staging studies as above. Subsequently, restaging will be carried out every 12 weeks unless, in the investigators' opinion, follow-up intervals need to be shorter. Studies to confirm a complete response or document progressive disease will be performed as needed. Patients will be allowed to continue study therapy after initial investigator-assessed RECIST 1.1/irRC-defined progression if they are deemed by the investigator to be deriving clinical benefit and tolerating study drug(s), as described in Section 8.3.

[figure not shown]

Figure 2. Study Design of preoperative nivolumab alone or in combination with ipilimumab. There are 2 arms to this study: A) Nivolumab monotherapy in resectable HCC; B) Combination nivolumab plus ipilimumab in resectable HCC.

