6.1.3 Administration of nivolumab

Patients in all two arms (a total of 30 will receive preoperative treatment with nivolumab as a 30 +/- 15-minute IV infusion on Day 1 of a treatment cycle every 2 weeks for arms A and B. Post-surgery adjuvant maintenance nivolumab will be given at 480 mg IV every 4 weeks until disease progression or intolerability. There will be no nivolumab dose escalations or reductions allowed. Patients in each arm may be dosed no less than 12 days from the previous dose. All post-surgical patients may be dosed no less than 12 days from the previous dose. If a subject cannot receive a following dose of the cycle within the designated time frame, it will be omitted and the next dose received will be considered Day 1 of the next cycle.

Nivolumab should be administered under the supervision of a physician experienced in the use of IV agents. Nivolumab is administered as an IV infusion only.

Calculate **Total Infusion Volume** as follows:

$(\text{Total nivolumab dose in mg} \div 10 \text{ mg/mL}) + \text{dilution volume} = \text{total infusion volume in mL}$

Calculate **Total Drug Concentration** as follows:

$\text{Total nivolumab dose in mg} \div \text{Total infusion volume nivolumab dose in ml} = \text{total infusion volume in mg/mL}$.

Total concentration cannot be below 0.35 mg/mL.

Calculate **Rate of Infusion** as follows:

$\text{Total infusion volume in mL} \div 30 \text{ minutes} = \text{rate of infusion in mL/min}$.

Example:

Flat dosing of 240 mg of nivolumab used.

The total infusion volume would be **24 mL** ($240 \text{ mg} \div 10 \text{ mg/mL} = 24 \text{ mL}$) if no dilution volume is added.

The total drug concentration would be **10 mg/mL** ($240 \text{ mg} \div 24 \text{ mL} = 10 \text{ mg/mL}$).

The rate of infusion would be **0.80 mL/min** in 30 minutes ($24 \text{ mL} \div 30 \text{ minutes} = 0.80 \text{ mL/min}$).

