8.2 Continued Treatment beyond Progression of Disease

Accumulating evidence indicates a minority of patients treated with immunotherapy may derive clinical benefit from continued treatment despite initial evidence of progressive disease [48]. For this reason, patients receiving nivolumab +/- [ipilimumab] will be permitted to continue study therapy beyond initial investigator-assessed RECIST 1.1-defined progression as long as they meet the 2 criteria listed below.

- Investigator-assessed clinical benefit, and
- Subject is tolerating study drug

The assessment of clinical benefit should take into account whether the subject is clinically deteriorating and unlikely to receive further benefit from continued treatment. All decisions to continue treatment beyond initial progression post-surgery must be discussed with the MDACC IND Office and documented in the study records.

Patients should discontinue study therapy upon evidence of further progression, defined as an additional 10% or greater increase in tumor burden from time of initial progression (including all target lesions and new measurable lesions).

New lesions are considered measurable at the time of initial progression if the longest diameter is at least 10 mm (except for pathological lymph nodes, which must have a short axis of at least 15 mm). Any new lesion considered non-measurable at the time of initial progression may become measurable and therefore included in the tumor burden measurement if the longest diameter increases to at least 10 mm (except for pathological lymph nodes, which must have an increase in short axis to at least 15 mm).

For statistical analyses that include the investigator-assessed progression date, patients who continue treatment beyond initial investigator-assessed, RECIST 1.1-defined progression will be considered to have investigator-assessed progressive disease at the time of the initial progression event.

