10.3.4.3 Immune related Response Criteria (irRC)

Table 5. irRC outcome measures [64]

New, measurable lesions	Incorporated into tumor burden
New, non- measurable lesions	Do not define progression (but precludes irCR)
Non-index lesions	Contribute to defining irCR (complete disappearance is required)
Complete response (CR)	Disappearance of all lesions in two consecutive observations not less than 4 weeks apart
Partial response (PR)	$\geq 50\%$ decrease in tumor burden compared with baseline in two observations at least 4 weeks apart
Stable disease (SD)	50% decrease in tumor burden compared with baseline cannot be established nor 25% increase compared with nadir
Progression of disease (PD)	$\geq 25\%$ increase in tumor burden compared with nadir (at any single time point) in two consecutive observations at least 4 weeks apart

Note: According to the irRC, disease progression of non-index lesions or appearance of new non-measurable lesions will not classify the subject as PD, and therefore the subject may stay in the study if it is the in the subject's best interest. A confirmatory tumor assessment may be performed no less than 4 weeks after the first indication of progression to provide additional data for the investigator to decide if the subject should stay in the trial or be discontinued due to clinical progression based on the investigator's decision.

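### Sections 5.3, 6.1.3 and 8.2 give conflicting rules for a patient whose disease progresses after surgery (off study, off drug, or continued on drug), with no order of precedence

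*Combined protocol and SAP*

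**What the plan says.** Three sets of statements in the current text deal with progression after surgery.

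- **Removal from the study.** Section 5.3: "Patients who show significant progression of disease post-operatively will be taken off study". Significant is not defined there, and it is not a category in the RECIST or irRC criteria of Section 10.3.4.
- **Drug ends at progression or recurrence.** Section 5.3 gives Arm A nivolumab "in the adjuvant setting until disease progression or for 2 years, whichever is sooner", and then states for both arms "until disease recurrence or for total of 2 years from first cycle, whichever is sooner". Section 6.1.3 gives post-surgical nivolumab as "480 mg IV every 4 weeks until disease progression or intolerability".
- **Drug may continue past progression.** Two paragraphs after the removal sentence, Section 5.3 says "Patients will be allowed to continue study therapy after initial investigator-assessed RECIST 1.1/irRC-defined progression", given clinical benefit and tolerance. It refers the reader to Section 8.3, which covers destruction of study drug. The rule itself is in Section 8.2, which sets the same two conditions, names post-surgery decisions, and requires them to be discussed with the IND Office and documented. The later stop is "Patients should discontinue study therapy upon evidence of further progression", meaning a further increase of 10% or more in tumour burden.

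Follow-up is set elsewhere. SAEs are collected to 100 days after the last dose (Section 11.1) and AEs to 100 days after dosing ends, or to the end of participation if that is later (Section 11.3). There is an end-of-treatment visit and a 30-day safety visit (Sections 5.3, 10.1.6 and 10.1.7). The schedules for both arms add follow-up visits with AE review, and 12-weekly survival contact after progression.

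**The concern.** A patient with a new liver lesion on the first surveillance scan after surgery falls under all three sets of statements: removed from the study, taken off drug, or kept on drug with further scans. Nothing says which governs, and an undefined adjective cannot sort the cases.

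Two things are at stake. The first is exposure: the date of the last dose, and with it the end of the AE window, depends on which sentence the site follows. The second is follow-up: a coordinator who takes off study at face value could stop collection that other sections require. Safety is the primary objective and is reported as AE and SAE incidence by arm (Section 12.2.1), so both should follow one rule in both arms.

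**Working it through.** The plan states no figure on this point, so there is none to reproduce. The check is a comparison of the text, then schedule arithmetic to size the effect on one patient.

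**Do the rules cover the same patients?** Yes. The removal sentence is about post-operative progression; the stopping sentences are about adjuvant drug; Section 8.2 explicitly covers continuation decisions after surgery. Progression is absent from the mandatory-withdrawal list in Section 8.0, so that list does not settle the matter.

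**Inputs.** Surgery at week 7, adjuvant start 4 weeks later, surveillance scan 8 weeks after surgery, nivolumab every 4 weeks, ipilimumab every 6 weeks for up to 4 doses in Arm B, and a limit of 2 years from first cycle (all Section 5.3). The 100-day windows are from Sections 11.1 and 11.3.

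**Assumptions.** First progression is seen at the 8-week post-operative scan, there are no delays, and under continuation no later stop occurs before 2 years. The continuation figures are therefore upper bounds.

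- Adjuvant start: 7 + 4 = week 11. Scan: 7 + 8 = week 15.
- Drug stopped at the scan: 1 adjuvant nivolumab dose (week 11), or 2 if the week 15 dose is given. Arm B: 1 adjuvant ipilimumab dose (week 11).
- Drug continued to 2 years from first cycle (week 1 + 104 = week 105): nivolumab at weeks 11, 15, ..., 103, so (103 − 11)/4 + 1 = 24 doses. Arm B ipilimumab at weeks 11, 17, 23 and 29: 4 doses.
- Shift in last dose: 103 − 15 = 88 weeks, or 103 − 11 = 92 weeks.
- End of the 100-day window (100/7 = 14.3 weeks): about week 25.3 or 29.3 if drug stops, against about week 117.3 if it continues. The shift is again 88 to 92 weeks.
- If the 2 years are counted from adjuvant start: last dose at week 111, (111 − 11)/4 + 1 = 26 doses, and a shift of 96 to 100 weeks.
- Imaging: the earliest irRC confirmation is 15 + 4 = week 19, and the next 12-weekly scan is 15 + 12 = week 27. Both fall after a week 15 off-study date.

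**What does not move.**

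- TOX counts related grade 3 or higher events in the first 6 weeks and long delays to surgery. The 13-of-15 success rule concerns events that delay the resection date (both Section 12.2.1). Neither depends on what happens after surgery.
- Section 8.2 dates RECIST progression at the first event whether or not treatment continues, so RECIST-based TTP and PFS event dates stay put.
- Section 12.2.2.2 also allows TTP by immune-related criteria, and irRC progression needs two observations at least 4 weeks apart. Only that version of TTP is exposed.

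**The case against.** The best reply is that this is a default and its exception: drug runs until progression, and Section 8.2, whose title announces treatment beyond progression, sets out when it may go on. That is a plausible intention and may well be the right reading of the stopping sentences. But no section states it, the pointer that should establish it leads to drug destruction, and it does not explain a sentence that takes patients off study.

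The second reply is that safety follow-up is protected elsewhere. This largely stands. The AE/SAE windows run from the last dose, not from study status. Section 11.1 excepts only withdrawal of consent, and the schedule footnote on SAEs keeps the 100 days even when new anticancer therapy starts. The end-of-treatment and 30-day visits and survival contact after progression all remain in the text. Off study could therefore mean off study treatment. A reader might infer that up to 100 days of AE data, or the primary endpoint, are lost. The documents do not support that: any loss depends on a site reading the sentence literally against the other sections.

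A reader might also infer that every irRC confirmation scan is lost. Section 10.3.4.3 makes the scan optional: "A confirmatory tumor assessment may be performed no less than 4 weeks after the first indication of progression". The irRC association is an exploratory objective, and the secondary objective names RECIST 1.1.

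Finally, continuation is not left to the investigator alone, since the IND Office must be consulted. Because the trial is open-label and continuation rests on a judgement of benefit, handling could differ by arm, but nothing in the documents shows that it does.

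**Conclusion.** The contradiction is real and worth correcting. It leaves open what happens to study drug at first post-operative progression, and it contains a phrase that, taken literally, contradicts the required follow-up.

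Its reach is limited to study-drug exposure, the end date of the AE window and hence descriptive AE/SAE incidence by arm, and any irRC-based TTP. Under the assumptions shown, one patient's adjuvant nivolumab could range from 1 or 2 doses to at most 24, adjuvant ipilimumab in Arm B from 1 to 4, and the end of the AE window by up to 88 to 92 weeks. TOX, the 13-of-15 rule and RECIST progression dates are untouched.

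The number of patients affected cannot be stated. It is tempting to take the recurrence of about 50% or more in the study rationale (Section 3.4.5) and say that half of the resected patients are affected. That figure has no time horizon, Section 3.2 gives up to 70% at 5 years, and adjuvant therapy lasts about 2 years at most. A patient who recurs more than 100 days after the last dose has no drug decision and no AE window left to lose.

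**What to change.** - Reconcile Sections 5.3 and 6.1.3 with Section 8.2 so that one rule, with its precedence stated, governs study drug at first progression after surgery. Which rule applies is for the sponsor to decide.
- Define significant progression in terms of the response criteria in use, or remove the adjective.
- Correct the cross-reference in Section 5.3 from 8.3 to 8.2.
- In the same section, replace taken off study with off study treatment, and state that the existing AE/SAE collection to 100 days, scheduled follow-up and survival contact continue.

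This is a wording amendment. The visits and contacts already exist in the schedules and in Section 11, so the cost is slightly more follow-up data entry. Enrolment has stopped, so the benefit is to patients still in adjuvant treatment or follow-up and to the clarity of the safety tables.
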